Our laboratory has pioneered the use of moderate intensity RMT regimens to provide respiratory muscle resistance training and address progressive neuromuscular weakness (Jones et al, 2011, 2014, 2016). Counteracting respiratory muscle weakness with moderate intensity exercise offers a biologically plausible mechanism to target progressive inspiratory and expiratory muscle weakness in ALS. This research will be the first study of a comprehensive RMT program targeting both inspiratory muscle weakness with IMT and expiratory muscle weakness with EMT in individuals with ALS. We will also utilize a well-defined, moderate intensity RMT regimen and pioneer the use of patient-reported RPE to monitor and regulate intensity. We will use telehealth visits to collect measures of respiratory muscle strength (maximum inspiratory pressure [MIP], maximum expiratory pressure [MEP]) in order to 1) reduce the number of on-site visits required by participants and 2) improve our ability to collect repeated measures of our primary outcomes. We will continue to use the novel modifications, methods, and technologies we have developed to allow progressive, individualized, and calibrated RMT to be delivered across the range of human performance. These include our calibration methodology to ensure accurate, precise RMT pressure-threshold resistance (Jones et al., 2014, 2016) and the Inspiratory Adapter 150 (US Patent Pending) to allow use of expiratory-type devices for IMT (EMST 150; Aspire LLC) and expand the range of resistance.

The results of this study will be used to refine our RMT in ALS treatment regimen, select appropriate outcome measures, and develop the statistical analysis plan for use in a future NIH grant application to further study RMT in ALS in a larger group of subjects.

4. Design & Procedures:

Participants will be recruited from the Duke ALS Clinic or referred through CT.gov or outside hospitals. Twelve adults will participate in a single- subject A₁-B-A₂ study involving 4 visits to Duke over 24 weeks (see **Figure 1**). The 6 week delayed start period represented by A₁ will establish baseline status prior to initiation of RMT and A₂ will determine detraining effects over 6 weeks of RMT withdrawal. Participants will complete four 3-week cycles of progressive RMT during the B phase. We will measure

Moderate intensity respiratory muscle training (RMT) in ALS

NCT04224961

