MIP and MEP weekly. To reduce participant burden and enhance our ability to obtain repeated measures, we will have the ability to obtain measurements of MIP and MEP during web-based telehealth visits.

Participants will complete a full assessment during the first study visit (M1), which may be performed in person or remotely via a web-based session, and receive training/instruction for obtaining MIP and MEP measurements at home with a portable, battery-powered digital pressure gauge manometer (MicroRPM Pressure Meter; Micro Direct). Prior to the pretest visit, participants who opt for remote visits will be mailed instructions for the home-based RMT regimen and the devices as well as a written treatment log. The pretest visit (M7) will include a full assessment after which RMT will commence. During the B phase, participants will complete 12-weeks of moderate intensity RMT, divided into four 3-week cycles, and participate in weekly web-based RMT therapy visits (M8-M18). Posttest assessment (M19) will occur immediately following completion of the 12-week RMT regimen. We will measure MIP and MEP during RMT withdrawal via web-based telehealth visits (M20-24). Following the fourth and final full assessment visit (M25), participants will return all equipment and will be offered the opportunity to initiate a clinical RMT regimen and receive follow-up care by Speech Pathology during future ALS Clinic visits.

Week	A1 (6 weeks)						B (12 weeks)												A2 (6 weeks)							
	0	1	2	3	4	5	6	7	8	9	10	11	12	13	14	15	16	17	18	19	20	21	22	23	24	
Measurement	M 1*	M 2 ^T	M 3 ^T	M 4 ^T	M 5 ^T	M 6 ^T	M 7*	M 8 ^T	M 9 ^T	M 10 ^T	M 11 ^T	M 12 ^T	M 13 ^T	M 14 ^T	M 15 ^T	M 16 ^T	M 17 ^T	M 18 ^T	M 19*	M 20 ^T	M 21 ^T	M 22 ^T	M 23 ^T	M 24 ^T	M 25*	
MIP	X	X	X	X	X	X	X	X	X	X	X	X	X	X	X	X	X	X	X	X	X	X	X	X	X	
MEP	X	X	X	X	X	X	X	X	X	X	X	X	X	X	X	X	X	X	X	X	X	X	X	X	X	
SNIP	X						X													X						X
PCF	X						X													X						X
ALSFRS	X						X													X						X
EAT-10	X						X													X						X
SF36	X						X													X						X
WHOQOL-BREF	X						X													X						X
CES-R	X						X													X						X
RMT							X	X	X	X	X	X	X	X	X	X	X	X	X	X	X	X	X	X	X	
	PRE						POS																			
	RMT Cycle 1						RMT Cycle 2						RMT Cycle 3						RMT Cycle 4							

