Participants will be asked to keep a paper log documenting the number of repetitions they complete each day as well as RPE and any pain they experience associated with home RMT.

See **Figure 4** and **Figure 5** for a detailed treatment decision tree and sequential list of treatment activities for each study visit.

10. Risk/Benefit Assessment:

Research participation is expected to be safe and well-tolerated based on our prior research using moderate intensity RMT in late-onset Pompe disease (Jones et al, 2011, 2014, 2016) and the relevant research in the ALS literature (Cheah et al., 2009; Pinto et al., 2012; Plowman et al., 2016). Multiple elements of our study design have been included to ensure rigorous safety monitoring and minimize risk including:

- Individualized, stepwise pressure-threshold resistance based on each subject's respiratory muscle strength and RPE;
- Weekly contact with the RMT clinician during the 12-week training period to foster adherence and assess for any negative side effects;
- A predetermined algorithm for modulating RMT intensity to ensure participant safety;
- Use of an experienced RMT clinician to conduct the RMT program with training and oversight by the PI;
- Calibration of RMT devices to ensure precise and accurate pressure-threshold resistance.

11. Costs to the Subject:

There are no costs to subjects to participate in this study.

12. Data Analysis & Statistical Considerations:

Descriptive statistics will be provided for all outcomes. Primary outcome measures of MIP and MEP will be analyzed using visual analysis of raw data in graphical format using the method described by Land and Gast (2014). Magnitude of change for our primary outcome measures will be determined using

Moderate intensity respiratory muscle training (RMT) in ALS

NCT04224961

Cohen's measure of effect size (d) as defined by the first equation for single-subject d provided by Busk and Serlin (1992). Simply stated, d is obtained by subtracting the mean of the first assessment from the mean of the second assessment, divided by the standard deviation of the first assessment. Effect size calculations will be determined to compare results from baseline (M0-M5) to withdrawal (M19-M24) and pretest (M7) to posttest (M18). We will use conservative interpretation guidelines for effect size calculations in which $d < 0.6$ is negligible, $d \geq 0.6$ modest, $d \geq 1.0$ large, and $d \geq 2.0$ very large.

13. Data & Safety Monitoring:

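### Neither planned effect size averages the weekly on-training readings of MIP and MEP; add one that compares M1-M7 with M17-M19 on the A1 SD

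*Combined protocol and SAP*

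**What the plan says.** Section 12 plans visual analysis of the raw MIP and MEP series, and then a d to express how large the change is. The numerator of d comes from "subtracting the mean of the first assessment from the mean of the second assessment", and the result is "divided by the standard deviation of the first assessment". Two comparisons are named: "Effect size calculations will be determined to compare results from baseline (M0-M5) to withdrawal (M19-M24) and pretest (M7) to posttest (M18").

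Section 4 sets out the data available. It plans to measure "MIP and MEP weekly", and Figure 1 shows 25 visits, M1 to M25. On the pretest: "The pretest visit (M7) will include a full assessment after which RMT will commence". During the training phase participants "participate in weekly web-based RMT therapy visits (M8-M18"). On the posttest: "Posttest assessment (M19) will occur immediately following completion of the 12-week RMT regimen". A1 is the delayed start before training and A2 is the withdrawal period. Section 3 gives two reasons for the telehealth readings: fewer on-site visits, and to "improve our ability to collect repeated measures of our primary outcomes".

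The labels in Section 12 do not match Figure 1: there is no M0, the posttest is M19 rather than M18, and withdrawal starts at M20. They need reconciling, but the present point holds under either labelling.

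**The concern.** An A-B-A design takes repeated readings in each phase so that a phase level can be estimated from more than one of them. Here the only d with several readings per side compares A1 with A2. That contrast describes what is retained after withdrawal, net of detraining and disease progression; it does not give the level reached in training. The d that does span training uses the fewest readings possible.

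Objective 2 in Section 2 is to make preliminary estimates of the effect on respiratory muscle strength, and Section 3 says the results will shape the analysis plan of a larger study. A noisy estimate, read against fixed cut-offs of 0.6, 1.0 and 2.0, can mislead that planning in either direction. In addition, a participant who leaves before posttest has no pretest-posttest d, even with up to 11 weekly training readings on file.

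**Working it through.** The plan states no standard error, power or target effect, so there is no figure of its own to reproduce.

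**1. Which visits enter a d** (Section 12 against Figure 1)
- Labels as written: M0-M5, M19-M24, M7 and M18. M0 does not exist, so 13 of 25 visits enter. Unused: M6, M8-M17, M25. M18 enters once, as an endpoint.
- Labels aligned to Figure 1: M1-M6, M20-M25, M7 and M19, so 6 + 6 + 1 + 1 = 14 of 25 enter. Unused: exactly M8-M18, which is 11/25 = 44%.

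Either way, no mean of training-phase readings enters a d.

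**2. The SD of a single value.** A sample SD divides by n - 1. With one value at M7 this is 0, so the second d cannot be computed as defined. It could be computed with several efforts per visit or with an SD borrowed from A1, but the plan specifies neither.

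**3. Standard error of the change.** Assumptions: constant SD s, and lag-1 autocorrelation ρ of 0, 0.5 or 0.7 with correlation ρ^h at h weeks apart. The variance of a mean of k weekly readings is (s²/k²)[k + 2Σ(k-h)ρ^h], with h from 1 to k-1.
- One visit v one visit (M7 v M19): variance 2(1 - ρ^12)s². This is 2.00s² at ρ = 0 and 0.5, and 2(1 - 0.0138) = 1.97s² at 0.7. The SE is 1.41s, 1.41s and 1.40s.
- M1-M7 v M17-M19, ρ = 0: 1/7 + 1/3 = 0.476, SE 0.69s; 0.476/2 = 0.24, so variance is 76% lower.
- ρ = 0.5: 0.348 + 0.611 = 0.959 (the covariance term is negligible), SE 0.98s; 0.959/2 = 0.48, 52% lower.
- ρ = 0.7: 0.518 + 0.753 - 0.018 = 1.253, SE 1.12s; 1.253/1.97 = 0.636, 36% lower (37% against 2.00).

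**4. Signal lost by averaging.** Assume a flat A1 and a gain G rising linearly from M7 (0) to M19 (G).
- M17-M19 keeps (10 + 11 + 12)/(3 × 12) = 33/36 = 92%.
- M8-M19 keeps (1 + ... + 12)/(12 × 12) = 78/144 = 54%.

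**5. Expected contrast divided by its SE, in units of G/s**

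| Contrast | ρ = 0 | ρ = 0.5 | ρ = 0.7 |
|---|---|---|---|
| M7 v M19 | 0.71 | 0.71 | 0.71 |
| M1-M7 v M17-M19 | 1.33 | 0.94 | 0.82 |
| M1-M7 v M8-M19 | 1.14 | 0.75 | 0.64 |

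**6. Effect on the plan's cut-offs.** This used 400,000 simulated participants with no true change, independent readings, no trend, and the SD taken from M1-M7.
- One v one reaches d ≥ 0.6, 1.0 and 2.0 in 35%, 26% and 10%.
- M1-M7 v M17-M19 does so in 21%, 10% and 1.4%.

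These rates are illustrative and would differ with autocorrelation or decline.

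**7. Trend within A1.** The mean of M1-M7 is centred on M4, three weeks before M7. A steady decline of c per week in A1 puts that mean 3c above the M7 level, so the gain measured from it is smaller by 3c than the gain from M7.

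**The case against.** The strongest reply is that visual analysis is itself a planned analysis of the primary outcomes, is standard for a single-subject design, and can use every reading from M8 to M18. Sections 9 and 10 show a second use: current MIP and MEP set the training target. This stands. A reader might infer from Section 12 that the weekly readings go unused, or that the whole assessment of training rests on two visits. The documents do not support that; it is true only of the effect sizes.

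A second reply is that the two d values are complementary: A1 v A2 addresses detraining, and pretest v posttest addresses gain. That is fair as to purpose, but it does not answer the imprecision of the second.

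A third is that the word mean in the definition may imply several efforts per visit. It may, but the plan does not say so, and a within-visit SD would be on a different scale from a week-to-week SD.

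It is also tempting to make A1 against all of B the remedy, since it has the smallest SE and retains early leavers. Steps 4 and 5 argue against this. It keeps only 54% of a linearly rising gain, is barely better than one v one at ρ = 0.5 (0.75 v 0.71), and is worse at 0.7 (0.64 v 0.71). Early leavers would contribute mostly early readings, which are not comparable with completers' values.

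Finally, this is a 12-person pilot with no hypothesis test, and the weekly data are retained whatever Section 12 says. That limits the weight of the point but does not remove it.

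**Conclusion.** The point holds for the planned effect sizes, under both the literal and the aligned visit labels. The size of the training effect is estimated from one visit at each end, by a d that has no SD if each visit gives one value.

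Replacing single visits with M1-M7 and M17-M19 lowers the variance of the change by 76% if readings are independent, 52% at autocorrelation 0.5 and about 36% at 0.7. Quoting 76% alone would be too favourable, because the documents give no SD or autocorrelation. Allowing for dilution under a linear rise, the proposed contrast beats the planned one at all three values (1.33, 0.94 and 0.82 against 0.71). These results assume constant SD, a flat A1 and a linear gain.

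This is an inexpensive improvement that should be made. It does not invalidate the pilot.

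**What to change.** In Section 12:

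- Add, as the main training effect size for MIP and for MEP, the mean of the pre-training readings (M1-M7, all taken before training starts) against the mean of the last readings of the training period (M17-M19). Report it in cmH2O and as d on the SD of the A1 readings (M1-M7).
- Keep the single-visit pretest-posttest change as supportive, and state which SD it uses and how many efforts per visit are kept.
- Optionally report A1 against all of B (M8-M19) as a secondary summary that retains early leavers. State that it captures only about 54% of a linearly rising gain and that early leavers' values are not comparable with completers'.
- Reconcile the visit labels with Figure 1.

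The cost is analysis wording only; every reading is already scheduled. The downsides are about 8% dilution if strength rises linearly to posttest, and a baseline mean that departs from the M7 level if there is a trend within A1. The supportive single-visit change and the plotted series will help to show the latter. The main contrast does not help participants who leave before M17.

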agrees, consent will be obtained. Consent will take place via phone script with eConsent, which is available via REDCap. This functionality provides the ability to consent remote participants or participants in clinic via tablets or touchscreen device. Participants will have the capability to sign electronically with a stylus, mouse, or finger. Once the consent form is submitted, participants will receive an email that includes a PDF attachment with a copy of the signed consent form. The PDF will be emailed to Health Information Management from REDCap for incorporation into Epic.

To minimize the possibility of coercion or undue influence, potential participants will be given ample time to ask questions and review the consent form. In addition, it will be stressed that participation in this study does not alter the treatment course and that participation is completely voluntary. The potential participant will be provided with the name and contact information for the study coordinator and the PI and the Duke IRB in the event of questions or concerns after reviewing the consent.

8. Subject's Capacity to Give Legally Effective Consent:

Legally effective informed consent will be obtained for all subjects. “Legally effective” means that the subject 1) has sufficient information to make a decision, 2) understands the consequences of a decision, (3) is able to make a decision, and 4) is able to communicate a decision. If a potential subject is incapable of informed decision-making, consent from their legally authorized representative (LAR) will not be sought, as the cognitive-communication skills necessary for informed consent are also necessary for participation in the research. The study will include high functioning ALS patients who may not be able to physically sign the ICF due to disease related muscle weakness so we will include an LAR and witness signature line.

9. Study Interventions:

During the 12-week intervention period, participants will complete a home-based RMT program and participate in weekly web-based RMT therapy sessions (M8-M18). RMT will be divided into four 3-week cycles. Participants will begin RMT immediately after completing assessments during the pretest visit (M7; see **Figure 1**). During this visit, participants will demonstrate ability to complete RMT repetitions successfully, and will be provided with all the necessary training and equipment to complete home RMT for the next 12 weeks.

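### Section 12 defines the effect size d with visit labels that conflict with the visit schedule (three of four), and names no SD for the single-visit pretest-posttest comparison

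*Combined protocol and SAP*

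**What the plan says.** Section 12 (Data Analysis & Statistical Considerations) measures the size of change in MIP and MEP with a single-subject Cohen's d. The difference between two assessment means is "divided by the standard deviation of the first assessment". The d values will "compare results from baseline (M0-M5) to withdrawal (M19-M24) and pretest (M7) to posttest (M18". They are then graded with cut-offs at 0.6, 1.0 and 2.0.

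Section 4 (Design & Procedures) numbers the visits differently:

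- First visit: "Participants will complete a full assessment during the first study visit (M1".
- Pretest: "The pretest visit (M7) will include a full assessment after which RMT will commence". Section 9 (Study Interventions) agrees: "Participants will begin RMT immediately after completing assessments during the pretest visit".
- Weekly therapy visits: M8 to M18, in sections 4 and 9.
- Posttest: "Posttest assessment (M19) will occur immediately following completion of the 12-week RMT regimen".
- Withdrawal: "We will measure MIP and MEP during RMT withdrawal via web-based telehealth visits (M20-24".
- End of withdrawal: "Following the fourth and final full assessment visit (M25".

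Figure 1 puts M1 at week 0 and M25 at week 24, with MIP and MEP measured at every visit.

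**The concern.** The sentence in section 12 decides which visits enter d. Apart from descriptive statistics, d is the only quantitative measure of change planned for the primary outcomes. Section 2 states the expected results in effect-size terms, and section 4 says the results will shape a future grant application and its analysis plan.

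Two things look wrong. First, the labels do not match the schedule, so the literal windows contain the wrong visits. Second, the pretest-posttest d needs an SD from a first assessment that is one visit, and the plan does not say where that SD comes from.

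The labels might be repaired differently by different analysts, or the SD might be chosen once the data are visible. Either could move a result across a cut-off.

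**Working it through.** The plan gives no figure to reproduce, so the check sets the labels against the schedule and then works out what follows.

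**1. Labels.** In Figure 1, visit M(w+1) falls at week w. The last column reads the section 12 labels as week numbers instead (Mk = week k).

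| Window | Section 12 | Schedule | Section 12 read as weeks |
|---|---|---|---|
| Baseline | M0-M5 | M1-M6 (weeks 0-5) | M1-M6, fits |
| Pretest | M7 | M7 (week 6) | week 7 = M8, does not fit |
| Posttest | M18 | M19 (week 18) | week 18 = M19, fits |
| Withdrawal | M19-M24 | M20-M25 (weeks 19-24) | M20-M25, fits |

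Taken as visit numbers, only M7 is right. Taken as week numbers, only M7 is wrong. No single numbering makes all four right.

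**2. Literal consequences.** These need no assumed values.

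- Baseline: M0 does not exist and M6 is dropped, leaving 5 visits instead of 6 (or instead of 7 if M7 is meant to count as baseline).
- Withdrawal: M19 to M24 is 0 to 5 weeks off training (mean 2.5), against 1 to 6 weeks (mean 3.5) for M20 to M25. The posttest is included and the 6-week visit is left out.
- Posttest: cycles start at M7, M10, M13 and M16, so the fourth ends at M19. Scheduled repetitions per muscle group total 4 × (125 + 250 + 375) = 3,000. By M18 they are 3 × 750 + 125 + 250 = 2,625 (87.5%), after 11 of 12 weeks.
- Adding one to every label would put the pretest at M8, after 125 scheduled repetitions per muscle group.

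**3. Effect of the windows on d.** Let L be the fall in cmH2O from M19 to M25 and s the weekly decline in A1.

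- The two withdrawal means differ by (M19 − M25)/6 = L/6.
- The mean baseline week is 2.0 for M1-M5 and 2.5 for M1-M6, so the baseline means differ by s/2.
- With the baseline SD held fixed, literal d minus corrected d = (L/6 − s/2)/SD.

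The documents give none of L, s or SD, so the values below are assumptions for illustration.

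| L | s | SD | Shift in d |
|---|---|---|---|
| 0 | 0 | any | 0 |
| 0 | 1 | 3 | −0.5/3 = −0.17 |
| 6 | 0 | 5 | 1/5 = +0.20 |
| 12 | 1 | 3 | 1.5/3 = +0.50 |
| 12 | 0 | 3 | 2/3 = +0.67 |
| 12 | −1 | 3 | 2.5/3 = +0.83 |

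A worked case, also assumed: baseline mean 60, SD 4, posttest 70, loss of 2 per week (L = 12, s = 0).

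- M19-M24: (70 − 2 × 2.5 − 60)/4 = 1.25, large on the plan's scale.
- M20-M25: (70 − 2 × 3.5 − 60)/4 = 0.75, modest.

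The pretest-posttest numerator using M18 is 11/12 of the M19 value if the gain is linear in weeks (8.3% too small). It is unchanged if strength plateaus before M18.

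**4. The SD for pretest-posttest.** With one recorded value at M7, a sample SD has zero degrees of freedom. If several efforts per visit are kept, an SD could be formed, but the plan does not say how many are kept or that their spread is the divisor. For an assumed gain of 8 cmH2O, SDs of 3, 5, 8 and 20 give d = 2.67, 1.60, 1.00 and 0.40. That runs from very large to negligible.

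**The case against.** The strongest reply is that this is one slip. Three labels look like leftover week numbers and convert exactly to the scheduled visits, while M7 is already correct. Section 12 also names its windows, and section 4 assigns pretest and posttest to M7 and M19 by name. A careful analyst would probably reach the right visits, and shifting every label by one would contradict sections 4 and 9. This is a fair account of how the error arose, but the analysis section still mixes two numberings.

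On the SD, the plan relies on a published equation and only paraphrases it. Repeated efforts within a visit might supply an SD, so it cannot be called mathematically impossible. That stands. The supportable claim is that the plan does not say which SD applies. A spread across participants would also yield a number, but not the single-subject d that the plan names.

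It is also true that the baseline-to-withdrawal d is not itself a detraining contrast, and that the weekly graphs run through M25 whatever section 12 says. The illustrative values of L, s and SD have no anchor in the documents, and +0.83 combines their extremes. These points limit the consequence. They do not remove the conflict.

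**Conclusion.** The concern holds with high confidence and should be fixed. Three of the four labels conflict with the schedule, and this follows from the running text of sections 4 and 9 without relying on the broken Figure 1 table. The SD for the pretest-posttest d is unspecified, and correcting the labels does not cure that.

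The misplacement of visits is certain. The effect on d is not. For assumed L of 0 to 12 cmH2O and SD of 3 to 5, the baseline-to-withdrawal d shifts by −0.17 to +0.67 if s lies between 0 and 1 cmH2O per week, and by −0.17 to +0.83 if baseline may also rise by up to 1 per week. These ranges hold the baseline SD fixed.

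The consequence is limited. d carries no test or decision rule, the visual analysis does not depend on it, the non-existent M0 signals the error, and d can be recomputed from the scheduled data.

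**What to change.** In section 12, after the investigators confirm this is what they intend:

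1. Relabel the comparisons as baseline (M1-M6) to withdrawal (M20-M25), and pretest (M7) to posttest (M19).
2. State whether M7, which is also measured before training starts, counts in the baseline mean and SD (M1-M6 or M1-M7).
3. Name the SD that divides the M7-to-M19 difference. One option is each participant's SD over the A1 baseline series. If a within-visit SD is intended, state how many efforts per visit are used.

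This takes two or three sentences. MIP and MEP are scheduled at all 25 visits, so no new data are needed. The SD should be fixed before the outcome data are examined.
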